3.2.3 Asthma Control Questionnaire-6

The ACQ-6 is a shortened version of the ACQ that assesses asthma symptoms (night-time waking, symptoms on waking, activity limitation, shortness of breath, wheezing, and use of short acting β_2 agonists), omitting the forced expiratory volume in 1 second measurement from the original ACQ score.

Patients are asked to recall how their asthma has been during the previous week by responding to 1 bronchodilator use question and 5 symptom questions. Questions are weighted equally and scored from 0 (totally controlled) to 6 (severely uncontrolled). The mean ACQ-6 score is the mean of the responses. The mean score will be missing if any symptom score is missing.

From Visit 2 onwards, the patient will complete the ACQ-6 at home every 1 week (\pm 2 days) until the EOT visit. The electronic Patient Reported Outcome (ePRO) device will be set up with functionality to collect unscheduled ACQ-6 assessments on site if required by Investigators at a visit.

The weekly ACQ-6 score will be monitored by Investigators, with an increase in ACQ-6 score of at least 0.5 from the value at Visit 2 indicating a potential **asthma deterioration**. If the ACQ-6 score at Visit 2 is missing, the first score recorded post-Visit 2 and pre-OCS reduction may be used as “baseline” for the 0.5-point increase. Note, however, that it will not be used to impute the baseline value for ACQ-6 analysis.

The outcome variables for ACQ-6 will be ACQ-6 scores at baseline (Visit 2), Visit 3, initial morning cortisol test, end of OCS reduction phase, and every 4 weeks from end of OCS reduction phase to end of maintenance phase (EOT visit); change from baseline in ACQ-6 score to Visit 3, initial morning cortisol test, end of OCS reduction phase, and end of maintenance phase (EOT visit); and change from the end of OCS reduction phase in ACQ-6 score to end of maintenance phase. ACQ-6, change from baseline, and change from the end of OCS reduction phase in ACQ-6 scores will also be assessed following any IPD visit. As the ACQ-6 is recorded weekly from Visit 2 to EOT, recorded scores may not coincide exactly with Visit 3 date, initial morning cortisol test, end of OCS reduction phase or EOT. For each of these timepoints, the ACQ-6 score recorded during the week (± 2 days) prior to the timepoint will be used for the outcome variable. The timing for the 4-weekly outcome variables (from the end of OCS reduction score to EOT) will be relative to the end of OCS reduction measurement, as per each patient's individual schedule. There will be no imputation for missing values.

Asthma control responder status will be evaluated as a supportive analysis. Patients will be categorized according to the following limits (Juniper et al 2005), where observed study time points include Visit 3, initial morning cortisol test (time point at which OCS dose equals 5 mg for 4 weeks), end of OCS reduction phase and end of maintenance phase (EOT visit):

- Improvement: Change from baseline in ACQ-6 score of ≤ -0.5
- No change: Change from baseline in ACQ-6 score of > -0.5 and $< +0.5$
- Deterioration: Change from baseline in ACQ-6 score of $\geq +0.5$

Asthma control responders will be defined as patients who had improvements based on the change from baseline in their ACQ-6 scores. Patients with no change or deterioration according to ACQ-6 score evaluation will be defined as non-responders. Patients with missing or non-evaluable ACQ-6 scores at a post-baseline assessment time point will be considered non-responders at the time point. (Note that baseline will be as defined in section 2.3 and will not be imputed (if missing) as for safety monitoring.)

Asthma control improvement status from the end of OCS reduction phase to end of maintenance phase will be evaluated as another supportive analysis. Patients will be categorized according to the following limits (Juniper et al 2005) at the end of maintenance phase:

- Improvement relative to end of OCS reduction phase: Change from the end of OCS reduction phase in ACQ-6 score of ≤ -0.5
- No change relative to end of OCS reduction phase: Change from the end of OCS reduction phase in ACQ-6 score of > -0.5 and $< +0.5$
- Deterioration relative to end of OCS reduction phase: Change from the end of OCS reduction phase in ACQ-6 score of $\geq +0.5$

Additionally, patients will be categorized according to their ACQ-6 defined asthma control status at baseline and post-baseline (Visit 3, initial morning cortisol test, end of OCS reduction phase, end of maintenance phase (EOT visit)) assessments using the following score thresholds (Juniper et al 2006):

- Well controlled: ACQ-6 score of ≤ 0.75
- Partially controlled: ACQ-6 score of >0.75 and <1.5
- Not well controlled: ACQ-6 score of ≥ 1.5

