#### **8.5.2.2 ACQ-6**

Change from baseline ACQ-6 score will be summarized by study visit using descriptive statistics and analyzed using a mixed model for repeated measures, with change from baseline in ACQ-6 score as the response variable, and baseline ACQ-6 score, baseline OCS dose, and baseline categories of serum eosinophil count as covariates. Results of the mixed model

analyses will be presented in terms of least square mean with 95% CI of change from Visit 2 in ACQ-6 score.

Asthma control responders will be evaluated as a supportive analysis outcome measure. Patients will be categorized according to the following limits ([Juniper et al 2005](#)), where observed study time points include, but are not limited to, Visit 3, initial morning cortisol test (time point at which OCS dose equals 5mg for 4 weeks), end of OCS reduction phase, and end of maintenance phase (EOT visit) from Visit 2:

- Improvement: Change from baseline in ACQ-6 score of  $\leq -0.5$
- No change: Change from baseline in ACQ-6 score of  $> -0.5$  and  $< +0.5$
- Deterioration: Change from baseline in ACQ-6 score of  $\geq +0.5$

Asthma control responders will be defined as patients who had improvements based on changes from baseline in their ACQ-6 scores. Patients with no change or deterioration according to ACQ-6 score evaluation will be defined as nonresponders. Patients with missing or nonevaluable ACQ-6 scores at a postbaseline assessment time point will be considered nonresponders at the time point.

Furthermore, patients will be categorized according to their ACQ-6 score-defined asthma control status at post Visit 2 assessments using the following score thresholds ([Juniper et al 2006](#)):

- Well controlled: ACQ-6 score of  $\leq 0.75$
- Partially controlled: ACQ-6 score of  $> 0.75$  and  $< 1.5$
- Not well controlled: ACQ-6 score of  $\geq 1.5$

Asthma control responders will be summarized in count and proportion with 95% Cis estimated using the Clopper-Pearson method. Patients with missing or nonevaluable ACQ-6 scores will be considered nonresponders.

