1.1.2 Secondary Objectives

Secondary Objective	Outcome measure

To assess the sustained reduction of daily OCS dose while not losing asthma control during approximately 6 months after the end of OCS down-titration (maintenance phase) in adult patients with severe eosinophilic asthma treated with benralizumab 30 mg SC
	
Key outcome measure
 
 • Change in daily OCS dose from the end of OCS reduction phase to the end of the maintenance phase (EOT visit) • Time to first increase in OCS dose during maintenance phase, after achieving the minimum OCS dose during the OCS reduction phase

To assess the effect of OCS down-titration protocol on asthma control in adult patients with severe eosinophilic asthma treated with benralizumab 30 mg SC
	
Key outcome measure
 
 • Asthma Control Questionnaire 6 (ACQ-6) scores at baseline (Visit 2), Visit 3, end of OCS reduction phase, and monthly from end of OCS reduction phase to end of maintenance phase (EOT visit) • Change from baseline in ACQ-6 to Visit 3, end of OCS reduction phase, and end of maintenance phase (EOT visit) • Responder analysis of ACQ-6 scores from Visit 2 through end of maintenance phase

To assess the effect of OCS down-titration protocol on quality of life in adult patients with severe eosinophilic asthma treated with benralizumab 30 mg SC
	
Key outcome measure
 
 • Change from baseline (Visit 2) in St. George's Respiratory Questionnaire (SGRQ) total scores to the end of maintenance phase (EOT visit) • Responder analysis of SGRQ total scores at the end of maintenance phase

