1.1.4 Exploratory Objective

Exploratory Objective	Outcome Measure
To investigate the contribution of genomic variants to the study outcomes	
 Association of common and rare genomic variants with patient responses
To assess early improvements in asthma status during the first 4 weeks of benralizumab treatment before initiation of OCS reduction	
 Patient Global Impression of Change (PGIC)
To assess the impact of OCS down-titration on blood eosinophil levels	Key outcome measure 
 Change from baseline blood eosinophils
To investigate biomarkers for predicting response to benralizumab	Key biomarker parameters 
 Serum samples at baseline for protein biomarkers Plasma for eosinophil-derived neurotoxin

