2.3 Baseline and change from baseline

In general, the last non-missing observation prior to the first dose of study treatment will serve as the baseline measurement. If there is no value prior to the first dose of study treatment, then the baseline value will not be imputed and will be set to missing.

Unless indicated otherwise, Visit 2 (Week 0) is the planned baseline visit, for all assessments carried out at the centre.

The absolute change from baseline is computed as (*visit value* – *baseline value*). Percent change from baseline is computed as $((\textit{visit value} - \textit{baseline value}) / \textit{baseline value}) \times 100\%$. If either a visit value or the baseline visit value is missing, the absolute change from baseline value and the percent change from baseline will also be set to missing. If baseline value is zero, the percent change will be set to missing.

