4.2.6.3 ACQ-6

ACQ-6 scores and change from baseline ACQ-6 score will be summarised using descriptive statistics at baseline (Visit 2) (for absolute ACQ-6 scores only), Visit 3, initial morning cortisol test (time point at which OCS dose equals 5mg for 4 weeks), end of OCS reduction phase, and every 4 weeks from end of OCS reduction phase to end of maintenance phase (EOT visit) (See section 3.2.3 for windowing at these time points). Change in ACQ-6 scores at the end of maintenance phase from the end of OCS reduction phase will be summarised in the same way.

Change from baseline in ACQ-6 score at Visit 3, initial morning cortisol test, end of OCS reduction phase and end of maintenance phase will be analysed separately using an analysis of covariance (ANCOVA) with change from baseline in ACQ-6 score as the response variable, and baseline ACQ-6 score, baseline OCS dose, and baseline categories of blood eosinophil count as covariates. Adjusted means will be calculated from the ANCOVA using the observed margins approach, in which the contribution of model factors to the estimate is

weighted proportionally to the presence of these factors in the data. Results will be presented in terms of least square mean with 95% CI of change from Visit 2 in ACQ-6 score.

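### No ACQ-6 change, category or shift runs from the pre-taper Visit 3 score to the end of OCS reduction, so the asthma-control objective is answered only indirectly

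*SAP*

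**What the plan says.** - **Objective.** SAP 1.1.2 and Protocol 2.2 set a secondary objective: "To assess the effect of OCS down-titration protocol on asthma control in adult patients with severe eosinophilic asthma" who are receiving benralizumab.
- **Timing.** Under SAP 1.2, patients take benralizumab for four weeks on their Visit 2 OCS dose. The first OCS reduction comes at Visit 3 at the earliest.
- **Expected early gain.** SAP 1.1.4 has an exploratory objective, measured by PGIC: "To assess early improvements in asthma status during the first 4 weeks of benralizumab treatment before initiation of OCS reduction".
- **Reference.** SAP 2.3: "the last non-missing observation prior to the first dose of study treatment will serve as the baseline measurement". SAP 3.2.3 then defines "change from baseline in ACQ-6 score to Visit 3, initial morning cortisol test, end of OCS reduction phase, and end of maintenance phase".
- **Model and categories.** The ANCOVA in SAP 4.2.6.3 uses the same reference: "Results will be presented in terms of least square mean with 95% CI of change from Visit 2 in ACQ-6 score". The improved, unchanged and deteriorated classes are cut at −0.5 and +0.5 from baseline (SAP 3.2.3; Protocol 8.5.2.2).
- **Second reference, maintenance phase only.** SAP 4.2.6.3: "Change in ACQ-6 scores at the end of maintenance phase from the end of OCS reduction phase will be summarised in the same way". The ±0.5 classes and the control-status shift are also planned from end of reduction to end of maintenance.
- **Outputs that need no baseline.** Absolute ACQ-6 scores and the three control-status classes are tabulated at Visit 2, Visit 3, the initial cortisol test, end of reduction and EOT.

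**The concern.** The objective asks what the down-titration protocol does to asthma control. The interval in which down-titration happens runs from Visit 3 to the end of OCS reduction, and no within-patient ACQ-6 analysis covers it. What does span the taper starts before benralizumab, so a gain in the first four weeks can offset a loss during the taper.

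On the SAP's own limits, a patient who gains 1.0 in induction and loses all of it is reported as no change. One who gains 1.5 and loses 1.0 is reported as an asthma control responder. At stake is whether the report can say how many patients lost control while OCS was withdrawn, and with what precision. The April 2021 SAP amendment gave the maintenance phase its own starting reference. The reduction phase, which the objective concerns, has none.

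**Working it through.** **1. Which intervals are analysed (SAP 3.2.3 and 4.2.6.3).**

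| Interval | Change | ±0.5 classes | Control-status shift |
|---|---|---|---|
| Visit 2 to Visit 3 | yes, ANCOVA | yes | yes |
| Visit 2 to initial cortisol test | yes, ANCOVA | yes | yes |
| Visit 2 to end of reduction | yes, ANCOVA | yes | yes |
| Visit 2 to EOT | yes, ANCOVA | yes | yes |
| End of reduction to EOT | yes, descriptive | yes | yes |
| Visit 3 to end of reduction | no | no | no |
| Visit 3 to EOT | no | no | no |

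**2. What a reader can recover.** In the same patients, mean change from Visit 3 to end of reduction equals mean change from Visit 2 to end of reduction minus mean change from Visit 2 to Visit 3. Its confidence interval needs Var(end) + Var(V3) − 2 Cov(end, V3), and the covariance is not among the planned outputs. Continuous scores are not imputed, so the two means may come from different patients. Two marginal control-status distributions do not show how many patients moved between classes.

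**3. Arithmetic on the ±0.5 rule.** Let G be the gain from Visit 2 to Visit 3 and L the loss from Visit 3 to end of reduction. The planned change is L − G.
- Classed as deteriorated if L − G ≥ 0.5, that is L ≥ G + 0.5.
- Classed as responder if L − G ≤ −0.5, that is L ≤ G − 0.5.
- With G = 1.0: a loss of 0.5 or less is still a responder, a loss above 0.5 and below 1.5 is no change, and only a loss of 1.5 or more is deterioration.

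**4. Illustration of size.** The documents give no means, SDs or correlation for ACQ-6 changes, so all inputs here are assumptions: normal changes, SD 0.8 in each interval, mean taper loss 0.25, correlation 0, 1,000,000 draws per row.

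| Mean induction gain | Lose ≥0.5 from Visit 3 | Deteriorated vs Visit 2 | Of those losing ≥0.5 from Visit 3: not classed as deteriorated | Of those: still responder |
|---|---|---|---|---|
| 0 | 37.7% | 41.3% | 27% | 4% |
| 0.5 | 37.8% | 25.3% | 49% | 12% |
| 0.75 | 37.7% | 18.9% | 59% | 19% |
| 1.0 | 37.7% | 13.4% | 69% | 28% |

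Varying the mean taper loss over 0, 0.25 and 0.5 and the correlation over 0 and −0.3, the share not classed as deteriorated is 45% to 84% for mean gains of 0.5 to 1.0, and 25% to 41% for a mean gain of zero. The zero-gain row is the reference case: that part comes from individual variation, not from an average induction benefit.

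**5. Precision of the missing analysis.** The plan's one sizing figure, 4.1 points around 50% at N = 600 (SAP 1.3), reproduces. Clopper-Pearson limits from the beta quantiles Beta(0.025; x, n − x + 1) and Beta(0.975; x + 1, n − x), with x = 300 and n = 600, lie 4.08 points from 50%. The point does not rest on that figure, but it shows what a Visit 3-referenced category would carry with complete data. A mean change would have a half-width of 1.96 × 0.8/√600 = 0.06 at an assumed SD of 0.8, or 1.96 × 1.2/√600 = 0.10 at an assumed SD of 1.2.

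**The case against.** A reader might infer that asthma control is judged solely against the pre-drug score, that the induction benefit conceals the loss, and that the objective goes unanswered. The documents do not support that. Absolute scores and control status are reported at Visit 3 and at end of reduction, the control classes with exact intervals. The Visit 2 to Visit 3 change is shown separately, so the induction gain is on display. Exacerbation counts and rates to end of reduction (SAP 3.3.2, 4.2.7.4) do not use an ACQ-6 reference at all.

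Visit 2 is also a defensible reference. The objective concerns patients treated with benralizumab, and deterioration is defined from Visit 2 in Protocol 4.2.2, 5.1.2.1 and 5.3.4.1. Someone 0.5 better than at entry really is better than before the programme. The trial is descriptive, tests no hypothesis, and nowhere attributes the Visit 2 change to OCS withdrawal alone.

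A Visit 3 reference does not isolate the taper either. The trial has one arm and benralizumab continues, so the change from Visit 3 still includes continuing drug effect. For patients on 5 mg at baseline, the initial cortisol test is done four weeks after the first dose and before any reduction, so that timepoint measures no taper for them.

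The size is assumed. The two changes share the Visit 3 score with opposite signs, so independence is doubtful.

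All of this stands, and it limits the claim. It does not supply a paired estimate over the taper or a count of patients who worsened in it.

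**Conclusion.** The gap holds in a limited form. No ACQ-6 change, ±0.5 category, ANCOVA or control-status shift runs from the pre-taper score to the end of OCS reduction, and the objective is therefore answered only indirectly. The G + 0.5 threshold follows from the SAP's own limits and needs no assumption. The 45% to 84% range does: it rests on assumed mean gains of 0.5 to 1.0, mean taper losses of 0 to 0.5, SD 0.8 and correlation 0 or −0.3, and should be read against 25% to 41% at zero mean gain.

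One could go further and make the Visit 3 comparison the analysis that answers the objective. That is a debatable choice of estimand which the documents do not require. A supportive analysis is enough.

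**What to change.** In SAP 3.2.3 and 4.2.6.3, add the last ACQ-6 score before the first OCS reduction (Visit 3 window) as a second reference. Make it a supportive analysis parallel to the existing end-of-reduction reference. From it, to end of OCS reduction and to EOT, report:

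- change in ACQ-6 with 95% CI;
- the ≤ −0.5 and ≥ +0.5 categories with Clopper-Pearson CIs;
- the shift in control status.

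Present these overall and by baseline OCS group. Report the same to the initial cortisol test only for patients with baseline OCS above 5 mg.

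Keep the Visit 2 analyses. Describe them, and SGRQ (measured at Visit 2 and EOT/IPD only), as the combined effect of benralizumab and OCS reduction. State that the Visit 3-referenced results still include continuing benralizumab effect. The investigators' Visit 2 monitoring rule is not changed.

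Cost: SAP wording and one extra set of tables. ACQ-6 is already collected weekly from Visit 2 to EOT, so no visits, patients or data items are added.

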3.2.4 St. George's Respiratory Questionnaire (SGRQ)

The change from baseline (Visit 2) in SGRQ total scores to the end of maintenance phase (EOT) is a secondary endpoint of this study. The SGRQ will be completed on site at the beginning of Visit 2 and EOT/IPD visit using the ePRO device.

The SGRQ is a 50-item PRO instrument developed to measure the health status of subjects with airway obstruction diseases (Jones et al 1991). The questionnaire is divided into 2 parts:

- Part 1 consists of 8 items that pertain to the severity of respiratory symptoms in the preceding 4 weeks;
- Part 2 consists of 42 items related to the daily activity and psychosocial impacts of the individual's respiratory condition.

The SGRQ yields a total score and 3 component scores (symptoms, activity, and impacts). The total score indicates the impact of disease on overall health status. This total score is expressed as a percentage of overall impairment, in which 100 represents the worst possible health status and 0 indicates the best possible health status. Likewise, the component scores range from 0 to 100, with higher scores indicative of greater impairment. Specific details on the scoring algorithms are provided by the developer in a user manual (Jones et al 2009).

A 4-point threshold will be used to define a response in SGRQ. If there is a ≥ 4 -point decrease from baseline in SGRQ total score, it will be defined as 'improvement'; if there is a ≥ 4 -point increase at EOT from baseline, it will be defined as 'worsening'; if the absolute change is less than 4 points at EOT, it will be defined as 'no change'. Response will also be assessed following any IPD.

The symptoms component score will be set to missing if there are >2 missing items; activity component score will be set to missing if there are >4 missing items; impacts component score will be set to missing if there are >6 missing items; and total score will be set to missing if one of the 3 component scores is missing.

To avoid incorrectly setting component and/or total scores to missing when items are logically skipped, the following items should **not** be considered as missing if logically skipped in the context of the subject's prior responses:

Question 6 (Length of worst attack of chest trouble):

If no severe or very bad, unpleasant attacks of chest trouble are reported in Q5, the length of the worst attack (Q6) will be logically skipped and should be imputed as zero, with the weight for Q6 remaining in the denominator.

Question 8 (Wheeze worse in the morning):

If the frequency of wheezing attacks is reported as 'None' in Q4, Q8 ('Wheezing worse in the morning') will be logically skipped and should be imputed as zero, with the weight for Q8 remaining in the denominator.

Question 14 (Medication does not help very much, Embarrassed using medication in public, Having side effects from medication, Medication interferes with life a lot):

If a patient is not taking any relevant medication, Q14 will be logically skipped. Therefore, if **all 4** responses are missing, all should be imputed as zero and the denominator for the component / total score(s) unchanged.

A missing SGRQ total score change at post-baseline time points will be considered as 'not evaluable'.

For the responder analysis of SGRQ, a responder will be defined as a patient who had 'improvement' (i.e. ≥ 4 -point decrease in SGRQ total score). Patients who had SGRQ total score changes defined as 'no change' or 'worsening' will be considered non-responders. If SGRQ total score change is not evaluable due to missing data, then the patient will also be treated as a non-responder.

3.3 Safety variables

Safety variables include:

- Disposition of adrenal function by morning cortisol and/or ACTH test
- Annualised asthma exacerbation rate and number (and percent) of patients with 0, 1, 2, etc exacerbations.
- Annualised asthma exacerbation rate leading to hospitalization or emergency room visit and number (and percent) of patients with 0,1, 2, etc exacerbations leading to hospitalization or emergency room visit
- AEs and SAEs
- Laboratory parameters
- Vital signs

- GTI

Safety analyses will use all available data, including data from unscheduled visits and repeated measurements.

[figure not shown]
Change from baseline to each post-treatment time point where scheduled assessments were made will be calculated for relevant measurements. Adverse events will be summarised by means of descriptive statistics and qualitative summaries.

No safety data will be imputed. The handling of partial/missing dates is detailed in Appendix 8.1.

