2.1.2 Full analysis set

All enrolled patients who received at least one dose of benralizumab will be included in the FAS, irrespective of their protocol adherence and continued participation in the study. Patients will be analysed irrespective of whether they prematurely discontinue, according to the intent-to-treat principle. Patients who withdraw from the study will be included up to the date of their study termination.

All efficacy and safety analyses will be performed using the FAS. For consistency, demographic and baseline characteristics will be presented using the FAS.

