3.3.2 Annualised asthma exacerbation rate

The number of asthma exacerbations and the annualised asthma exacerbation rate will be derived and summarized for the on-study period to end of OCS reduction phase at DBL1, on-study period during maintenance phase, and the overall on-study period at DBL2. On-study period to end of OCS reduction phase is defined as from the day of the first dose of study treatment to the end of OCS reduction phase; on-study period during maintenance phase is defined as from the start of the maintenance phase to the scheduled follow-up visit of the main study; and the overall on-study period is defined as from the day of the first dose of study treatment to the scheduled follow-up visit of the main study. A patient will be considered as having an asthma exacerbation if he/she starts a course of SCS (oral, parenteral) due to asthma, or has an emergency room/urgent care visit or a hospitalisation due to asthma.

The annualised asthma exacerbation rate will be calculated using the time-based approach. Annual asthma exacerbation rate = $365.25 \times \text{total number of exacerbations} / \text{total duration of follow-up (days)}$.

The number and annualised rate of exacerbations requiring hospitalisation or an emergency room visit will also be derived and summarised for the on-study period to end of OCS reduction phase at DBL1, on-study period during maintenance phase, and the overall on-study period at DBL2.

As a sensitivity analysis, annualised exacerbation rates will also be calculated using total duration of follow-up less days with exacerbations (+ 7 days per exacerbation) as the denominator.

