Continuous variables will be summarised using the mean, two-sided 95% CI of the mean, the standard deviation, median, minimum value, and maximum value. Categorical variables will be summarised using frequency counts and percentages, as well as a two-sided 95% CI for proportions computed using the exact Clopper-Pearson method. All patients in the corresponding analysis set will be considered the denominator. Time to event data will be summarised using median and 25th and 75th percentiles with 95% CIs. Data will be listed in patient level data listings.

No formal hypothesis will be tested in this study, and no multiplicity adjustment will be applied in the statistical analysis. No imputation will be performed beyond the approach defined for outcome measures in Section 4.2.6.3.

Due to the single-arm study design, external data sources may be used to contextualize any change seen in asthma control, asthma exacerbation rate, or other safety endpoints in patients treated with benralizumab following reduction of OCS. Any data sources identified, together with planned analyses, will be described in a separate analysis plan.

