4.2.4 Study treatment administration

Study treatment exposure and compliance will be calculated for the period to end of OCS reduction phase at DBL1, during maintenance phase, and the overall study period at DBL2.

Exposure to end of OCS reduction phase is calculated in days as (last dose of IP date - first dose of IP date + 1) if patient's last dose is prior to end of OCS reduction phase; or as (end of OCS reduction phase date - first dose of IP date + 1) otherwise.

Exposure during maintenance phase is calculated in days as (last dose of IP date - start date of maintenance phase + 1) if patient's last dose is after the end of OCS reduction phase; or 0 otherwise.

Duration of investigational product administration for the overall study period will be calculated in days as:

$$\text{Last dose date of IP} - \text{first dose date of IP} + 1$$

and will be summarised for all patients in FAS and for each subgroup defined in section 4.1 except the subgroups by patient's AI status at the end of OCS reduction phase or at the end of maintenance phase.

Study treatment compliance will be summarised for the full analysis set and calculated as:

$$\text{Study treatment compliance} = (\text{total doses administered} / \text{total doses expected}) \times 100.$$

Total number of doses expected will be calculated for the three study periods as defined for exposure. It includes all visits with protocol scheduled IP administration on or before a subject's IP discontinuation to end of OCS reduction phase or during maintenance phase, or treatment complete date (for the overall study period).

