4.2.7 Safety outcome variables

All safety variables will be summarised using the full analysis set (FAS) and data presented as a single group.

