4.2.7.4 Asthma exacerbations

The number of asthma exacerbations, number of patients with at least one exacerbation, number of exacerbations per patient, duration of exacerbation, number of exacerbations requiring hospitalization, number of exacerbations requiring emergency room visits, and number of exacerbations requiring OCS/Systemic Corticosteroid use will be summarised for the three study periods as defined in section 3.3.2. All asthma exacerbations will be listed by patient.

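### Maintenance-phase exacerbation counts are taken over the whole FAS, so patients who never entered maintenance dilute the percentage with at least one exacerbation

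*SAP*

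**What the plan says.** SAP 3.3 names as a safety variable the "Annualised asthma exacerbation rate and number (and percent) of patients with 0, 1, 2, etc exacerbations", with a parallel item for exacerbations leading to hospitalisation or an emergency room visit.

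SAP 3.3.2 sets three reporting periods: up to the end of OCS reduction at the first database lock, then "on-study period during maintenance phase, and the overall on-study period at DBL2". It fixes the window for the second of these: "on-study period during maintenance phase is defined as from the start of the maintenance phase to the scheduled follow-up visit of the main study". SAP 4.2.7.4 lists what is summarised in each period, including the "number of patients with at least one exacerbation, number of exacerbations per patient".

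Three general rules set the denominator:

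- SAP 4.2.7: "All safety variables will be summarised using the full analysis set (FAS) and data presented as a single group".
- SAP 4.1: "All patients in the corresponding analysis set will be considered the denominator".
- SAP 2.1.2: "All enrolled patients who received at least one dose of benralizumab will be included in the FAS, irrespective of their protocol adherence".

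SAP 4.2.1 counts entry into the maintenance phase as its own disposition category, so the plan foresees that some FAS patients will not get there. No section limits the maintenance-phase exacerbation summary to those who did.

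**The concern.** The maintenance window opens when a patient starts maintenance. Someone who withdraws during induction or OCS reduction has no such window and cannot have a maintenance-phase exacerbation. Under the general rules that person still adds one to the denominator.

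The SAP does write specific rules for similar situations elsewhere. PGIC percentages use completed assessments (4.2.8.1). Time to first OCS increase includes only patients who entered the reduction phase (4.2.6.2). The final maintenance OCS dose is set to missing for patients who withdraw during reduction (3.2.1). Exacerbation counts have no such rule, so the default applies.

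What is at stake is the description of how patients fare once OCS has been reduced, which the protocol (section 1.2) gives as the reason for a longer maintenance phase. More early withdrawal would make the share with an exacerbation look smaller. The same output would also place a rate based on time at risk beside percentages that include people never at risk.

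**Working it through.** **The plan's own figure.** The documents give no expected exacerbation-free percentage and no expected number of non-entrants. The only sizing figure is the Clopper-Pearson distance of ±4.1 points at 50% with 600 patients (SAP 1.3). Recomputed from beta quantiles it is −4.1/+4.1. Fifteen of the 16 cells of SAP Table 1 match to one decimal. The exception, 600 patients at 60%, gives −4.0/+3.9 against −4.0/+4.0 and has no bearing here. That precision was set for the primary OCS endpoint, so it gives scale only.

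**Inputs.** N = 600 (SAP 1.3). Both of the following are assumptions:

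- d = share of the FAS that never enters maintenance
- p = exacerbation-free share among entrants

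**Formulas.**

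- At least one exacerbation, among entrants: 1−p
- At least one exacerbation, FAS denominator: (1−d)(1−p), too low by d(1−p) however non-entrants are coded
- Zero exacerbations, FAS denominator, non-entrants counted as zero: p(1−d)+d, too high by d(1−p)
- Zero exacerbations, FAS denominator, non-entrants uncoded: p(1−d), too low by dp

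**Worked case, d = 10%, p = 70%.** There are 60 non-entrants and 540 entrants, of whom 378 are exacerbation-free and 162 are not.

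- At least one: 162/540 = 30.0% among entrants; 162/600 = 27.0% on the FAS
- Zero: 378/540 = 70.0% among entrants; (378+60)/600 = 73.0% if coded zero; 378/600 = 63.0% if uncoded

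**Varying d at p = 70%** (among entrants: 30.0% with at least one, 70.0% with zero).

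| d | Entrants | At least one, FAS | Zero, coded 0 | Zero, uncoded |
|---|---|---|---|---|
| 5% | 570 | 28.5% | 71.5% | 66.5% |
| 10% | 540 | 27.0% | 73.0% | 63.0% |
| 15% | 510 | 25.5% | 74.5% | 59.5% |

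**Wider range, d = 2–20%, p = 50–90%.** The percentage with at least one exacerbation is too low by 0.2 to 10.0 points. The zero row is off by +0.2 to +10.0 points if non-entrants are coded zero, or by −1.0 to −18.0 points if they are uncoded.

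**Annualised rate.** SAP 3.3.2 uses 365.25 × exacerbations / days of follow-up. A non-entrant adds no exacerbations and no maintenance days, so the maintenance-phase rate does not change.

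**The case against.** A reader might infer that non-entrants are counted as having zero exacerbations, so that the exacerbation-free percentage is too high. The documents do not establish this. No section assigns them zero. SAP 3.3 rules out imputing safety data, and the nearest comparable maintenance value, the final OCS dose in 3.2.1, is set to missing. If non-entrants are left uncoded, the exacerbation-free percentage is too low. Zero is a likely programming result, because a patient without event records usually counts as zero and there is no row for not having entered. It remains an inference.

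SAP 4.2.4 does not settle the matter. Maintenance exposure is positive if the last dose "is after the end of OCS reduction phase; or 0 otherwise", but that is a drug-exposure formula tied to the last dose date, not a rule for exacerbation counts.

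Further objections carry weight:

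- The declared key outcomes for exacerbations (SAP 1.1.3) are the annualised rates, which are sound. Sustained control is addressed mainly by the secondary endpoints on OCS dose and ACQ-6.
- Patients whose reduction fails, including after a second exacerbation, still enter maintenance (SAP 1.2). Non-entrants are mainly people who leave before reduction ends, for reasons the documents do not specify. It cannot be assumed that they were doing badly.
- The percentage by period is partly inferred. The item in 3.3 names no period, and 4.2.7.4 lists numbers. Percentages follow from the rule in 4.1 that categorical variables are shown as counts and percentages. For hospitalisation or emergency room exacerbations, 3.3.2 and 4.2.7.4 give event counts and rates by period, not patient counts.
- Disposition and patient-level listings would let a careful reader recompute the figure.

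These points limit the importance of the problem. They do not remove the dilution, since nothing overrides the FAS denominator for maintenance.

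**Conclusion.** The point holds in a limited form. Followed as written, the SAP gives a maintenance-phase percentage with at least one exacerbation that is below the value among patients at risk whenever any FAS patient fails to enter maintenance. This does not depend on how those patients are coded. The zero-exacerbation percentage is also distorted, but its direction cannot be read from the documents.

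The size rests entirely on assumed non-entry and exacerbation-free shares. At 5–15% non-entry with 70% of entrants exacerbation-free, the understatement is 1.5 to 4.5 points. Because patients who fail reduction still enter maintenance, actual non-entry may be small. The table is descriptive, no hypothesis is tested and the annualised rates stand, so severity is low to moderate.

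**What to change.** Add one sentence to SAP 3.3.2 or 4.2.7.4. For the maintenance period only, patient counts, percentages and exacerbations per patient are computed in FAS patients who entered the maintenance phase, using the number already produced under 4.2.1. The number who never entered is printed beside them. Apply the same rule to hospitalisation or emergency room exacerbations wherever patient counts are tabulated. Keep the FAS denominator for the period to the end of OCS reduction and for the overall period.

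The cost is one sentence and one denominator flag. The revised percentage conditions on a post-baseline event, entry into maintenance. It also does not adjust for unequal follow-up: an entrant who withdraws soon after entry without an event still counts as exacerbation-free. It should therefore be read beside the time-based rate.
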